# 8.2.4 Grading and Attribution

## 8.2.4.1 Grading Criteria

The study site will grade the severity of AEs experienced by CIT study subjects according to the criteria set forth in the *CIT-TCAE*... This document provides a common language to describe levels of severity, to analyze and interpret data, and to articulate the clinical significance of all AEs.

AE severity will be graded on a scale from 1 to 5 according to the following standards in the *CIT-TCAE* manual:

Grade 1 = Mild AE

Grade 2 = Moderate AE.

Grade 3 =Severe and undesirable AE.

Grade 4 = Life-threatening or disabling AE.

Grade 5 = Death.

AEs, not included in the CIT-TCAE listing, should be recorded and their severity graded from 1 to 5 according to the General Grade Definition provided below:

Table 3: General severity definition of adverse event

Grade 1	Mild	Transient or mild discomforts (< 48 hours), no or minimal medical intervention/therapy required, hospitalization not necessary (non-prescription or single-use prescription therapy may be employed to relieve symptoms, e.g. , aspirin for simple headache, acetaminophen for post-surgical pain).
Grade 2	Moderate	Mild to moderate limitation in activity some assistance may be needed; no or minimal intervention/therapy required, hospitalization possible.
Grade 3	Severe	Marked limitation in activity, some assistance usually required; medical intervention/therapy required hospitalization possible.
Grade 4	Life- threatening	Extreme limitation in activity, significant assistance required; significant medical/therapy intervention required hospitalization or hospice care probable.
Grade 5	Death	Death.

All AEs will be reported and graded, by the PI or designee whether they are or are not related to disease progression or treatment.

#### 8.2.4.2 Definition of Attribution

The relatedness, or attribution, of an AE to islet transplantation, which includes the transplant procedure and/or the islet product, the secondary investigational agent (Rituximab), or to the immunosuppression and/or infection prophylaxis will be determined by the site investigator. The site investigator will also record the determination of attribution on the appropriate eCRF and/or SAE report form. The relationship of an AE (attribution of AE) to islet transplantation (islets or transplant procedure), Rituximab, or immunosuppression/infection prophylaxis will be defined by using the descriptors provided below.

Table 4: Attribution of Adverse Events

Code	Descriptor	Definition				
UNRELATED CATEGORY						
1	Unrelated	The AE is clearly not related to allogeneic islets; the islet transplant procedure; immunosuppression or infection prophylaxis.				
RELATED CATEGORIES						
2	Unlikely	The AE is doubtfully related to allogeneic islets; the islet transplant procedure; immunosuppression or infection prophylaxis.				
3	Possible	The AE may be related to allogeneic islets; the islet transplant procedure; immunosuppression or infection prophylaxis.				
4	Probable	The AE is likely related to allogeneic islets; the islet transplant procedure; immunosuppression or infection prophylaxis.				
5	Definite	The AE is clearly related to allogeneic islets; the islet transplant procedure; immunosuppression or infection prophylaxis.				

For additional information and a printable version of the CIT-TCAE manual, consult the CIT website: http://isletstudy.org.

# 8.3 Serious Adverse Events

# **8.3.1** Collecting Procedure

SAEs will be collected following the subject's signing of the enrollment consent until 30 days after the subject completes or withdraws from the study. SAEs will be followed until the time the event is resolved, stabilized, or until 30 days after the subject completes or withdraws from the study, whichever comes first.

In addition, SAEs that occur after this time period that are believed to be certainly, probably, or possibly related to the investigational agent will be collected.

# 8.3.2 Recording Procedure

SAEs will be recorded on the AE eCRF.

If the investigator believes that an SAE is not related to the investigational product, but is potentially related to the conditions of the study (such as withdrawal of previous therapy, or complication of a trial procedure), the relationship should be specified in the narrative section of the SAE page of the eCRF.

# 8.3.3 Reporting Procedure

The following process for reporting an SAE ensures compliance with the ICH guidelines and 21CFR §312.32.

## 8.3.3.1 Reporting Criteria From Sponsor to Health Authority

After the SAE has been assessed, the event will be reported to the appropriate health authorities in the required manner based on the following criteria:

- **No reporting.** This requirement applies if the AE is deemed not serious by the DCC medical reviewer and, NIDDK/NIAID medical monitor.
- **Standard reporting** (*i.e.*, should be included in the investigational new drug [IND] annual report to the health authorities). This requirement applies if the AE is classified as any of the following:

Serious, expected, and drug related.

Serious, expected, and *not* drug related.

Serious, *unexpected*, and not drug related.

• **Expedited reporting.** This requirement applies if the AE is considered serious, unexpected, and drug related as defined in 21 CFR 312.32. This type of SAE must be reported by the sponsor to the appropriate health authorities within 15 days; fatal or lifethreatening events must be reported within 7 days.

# 8.3.3.2 Reporting Timeline– From the Site to the DCC

When an investigator identifies an SAE (as defined in section 8.1.2), he or she must notify the DCC Safety Reporting Center within 24 hours of discovering the event by submitting an initial electronic SAE CRF. In the event that the eCRF cannot be submitted (*i.e.* computer failure), the site must fax a paper SAE report to the DCC within 24 hours of discovering the event.

AEs as defined in Section 8.1.1 other than serious AEs will be reported to the DCC by the sites on at least a monthly basis.

# 8.3.3.3 Reporting Timeline – From the DCC to the Sponsor and Health Authorities

The DCC is responsible for notifying the sponsor within 2 business days of receiving the report by the clinical site. The sponsor is responsible for disseminating reports to the health authorities, and all investigators in the study and the manufacturer of the secondary study drug. SAEs per 21 CFR 312.32 definitions, except elective hospitalizations, will be reported to the Health Authority by the study sponsor (NIAID) in accordance with applicable regulations.

# 8.3.3.4 Notifying the Data and Safety Monitoring Board

The NIDDK/NIAID will provide the DSMB with listings of all AEs/SAEs on an ongoing basis at least yearly.

# 8.3.3.5 Notifying the Institutional Review Board and Ethics Committee

The investigator will ensure the timely dissemination of SAE information, including expedited reports, to the IRB and Ethics Committee (EC) in accordance with applicable regulations and guidelines.

# 8.3.3.6 Pregnancy

Sexually-active women of child bearing potential (WOCBP) must use an effective method of birth control during the course of the study, in a manner such that risk of failure is minimized. Prior to study enrollment, WOCBP must be advised of the importance of avoiding pregnancy during trial participation and the potential risk factors for an unintentional pregnancy. The subject must sign an informed consent form documenting this discussion.

In addition, all WOCBP should be instructed to contact the investigator immediately if they suspect that they might be pregnant (*e.g.*, missed or late menstrual period) at any time during study participation.

## 8.3.3.7 Reporting Pregnancy as a Serious Adverse Event

Any pregnancy that occurs during a clinical study that is using an investigational drug must be reported to the DCC utilizing the SAE report form. This report is *for tracking purposes only*. All pregnancies that are identified during the study must be followed to conclusion and the outcome of each must be reported. The investigator should be informed immediately of any pregnancy and should instruct a pregnant subject to stop taking study medication. The investigator should report all pregnancies within 24 hours (as described in section 8.3.3.2) using the SAE report form. The investigator should counsel the subject and discuss the risks of continuing with the pregnancy and the possible effects on the fetus. Monitoring of the subject should continue until the conclusion of the pregnancy, and a follow-up SAE report form detailing the outcome of the pregnancy should be submitted.

# 8.4 Updating Source Documentation

Documents describing the safety profile of a drug, such as the investigator's brochure, will be amended as needed by the study drug manufacturer to ensure that the description of safety information adequately reflects any new clinical findings. Until these documents are updated, expedited reporting will be required for additional occurrences of a reaction.

#### 9. MECHANISTIC ASSAYS

The following specimens may be used in future assays to reevaluate biological responses as research tests are developed over time. Study subjects will be informed that they may be approached about additional clinical evaluations or studies that have received the full approval of the NIAID/NIDDK as new evaluations are identified. If additional evaluations are determined to be desirable, this protocol (and other appropriate study documents, *e.g.*, the informed consent and the statistical analysis plan [SAP]) will be amended and submitted to the appropriate regulatory authorities, ECs, and IRBs for approval. Each subject's signature will be obtained on the revised informed consent form before additional evaluations are performed. The specimens from these evaluations may be stored up to the end of the contract—approximately 5 years, or longer if the contract is extended.

# 9.1 Metabolic Testing

# 9.1.1 Study Endpoints

Designated primary and secondary endpoints will be employed to compare subjects in this study to the group in CIT-07. Because the assessment of islet graft function is dependent on complex physiologic relationships between the graft and its recipient, no single test adequately addresses the viability of the transplant. Therefore, insulin-independence will be used as a clinically relevant measure of islet graft function for the primary endpoint, and additional stimulatory tests of islet graft function utilizing meal (MMTT) and glucose (FSIGT) challenges will be performed to assess secondary endpoints. Also, the effect of islet graft function on glycemic control (HbA1c), glycemic lability (MAGE and LI), hypoglycemia (Clarke and HYPO scores), glucose variability (CGMS), and QOL will be assessed as additional secondary endpoints.

#### 9.1.2 Metabolic Assessments

All subjects will use a study provided One Touch® Ultra glucometer for measuring capillary glucose levels. The timing of all metabolic assessments is provided in the Schedule of Events (Appendix 1).

## 9.1.2.1 Insulin Requirements

Subjects will record their total daily insulin dose on self-monitoring diaries. Subject should be given exogenous insulin as needed to maintain fasting capillary glucose levels ≤140 mg/dL (7.8 mmol/L) at a minimum of 4 out of 7 days a week; 2-hour post-prandial capillary glucose levels should not exceed 180 mg/dL (10.0 mmol/L) more than 3 times per week.

### 9.1.2.2 Glycemic control

Glycemic control will be assessed by HbA1c (%), which will be analyzed centrally at the University of Washington.

## 9.1.2.3 Glycemic lability

Glycemic lability will be assessed by both the MAGE and the LI.

The MAGE requires 14 – 16 BG measurements over two consecutive days taken before and 2-hours after breakfast, lunch, and dinner, and at bedtime with an optional measurement at 3 AM. A glycemic excursion is calculated as the absolute difference in peak and subsequent nadir (or vice versa) glucose values, with the direction (peak to nadir versus nadir to peak) determined by the first quantifiable excursion in the two day period. All excursions > 1 S.D. of the 7 – 8 glucose readings for the day in which they occurred qualify for the analysis, where they are summed and divided by the number of qualified excursions to give the MAGE in mmol/L (or mg/dL) glucose. A MAGE >11.1 mmol/L (200 mg/dL) is indicative of marked glycemic lability.

The LI requires 4 or more daily BG measurements over a 4 week period and is calculated as the sum of all the squared differences in consecutive glucose readings divided by the hours apart the readings were determined (range 1 to 12 hours) in mmol/L/hr·wk. A LI greater than or equal to the 90th percentile (433 mmol/L/hr·wk) of values derived from an unselected group of T1D patients is evidence for severe glycemic lability.

## 9.1.2.4 Hypoglycemia

An episode of severe hypoglycemia is defined as an event with one of the following symptoms: memory loss; confusion; uncontrollable behavior; irrational behavior; unusual difficulty in awakening; suspected seizure; seizure; loss of consciousness; or visual symptoms, in which the subject was unable to treat him/herself and which was associated with either a blood glucose level <54 mg/dL (3.0 mmol/L) or prompt recovery after oral carbohydrate, IV glucose, or glucagon administration.

In addition, composite indices of hypoglycemia frequency, severity, and symptom recognition will be assessed by both the Clarke survey and the HYPO score.

The Clarke survey involves subject completion of eight questions scored by the investigator according to an answer key that gives a total score between 0 and 7 (most severe), where scores of 4 or more indicate reduced awareness of hypoglycemia and increased risk for severe hypoglycemic events.

The HYPO score involves subject recording of BG readings and hypoglycemic events (BG <3.0 mmol/L [54 mg/dL]) over a 4-week period and recall of all severe hypoglycemic episodes in the previous 12 months. A HYPO score greater than or equal to the 90th percentile (1047) of values derived from an unselected group of T1D patients indicates severe problems with hypoglycemia.

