# **Secondary Endpoints**

# **Efficacy Endpoints**

At  $75 \pm 5$  days following the first and final islet transplant:

- Proportion of insulin-independent subject
- The percent reduction in insulin requirements
- HbA1c
- Mean amplitude of glycemic excursions (MAGE)
- Glycemic lability index (LI)
- Ryan hypoglycemia severity (HYPO) score
- Basal (fasting) and 90-min glucose and c-peptide derived from the mixed-meal tolerance test (MMTT)
- β-score
- C-peptide: (glucose X creatinine) ratio
- Acute insulin response to glucose (AIRglu), insulin sensitivity, and disposition index derived from the insulin-modified frequently-sampled intravenous glucose tolerance (FSIGT) test
- Glucose variability and hypoglycemia duration derived from the continuous glucose monitoring system®
- Quality of life measures

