#### 3.1.1 Secondary Endpoints

#### **Efficacy Endpoints**

At  $75 \pm 5$  days following the first and final transplant(s):

- The proportion of insulin-independent subjects
- The percent reduction in insulin requirements
- HbA1c
- MAGE
- LI
- Ryan hypoglycemia severity (HYPO) score
- Basal (fasting) and 90-min glucose and c-peptide derived from the mixed-meal tolerance test (MMTT)
- β-score
- C-peptide: (glucose X creatinine) ratio
- Acute insulin response to glucose (AIRglu), insulin sensitivity, and disposition index derived from the insulin-modified frequently-sampled IV glucose tolerance (FSIGT) test
- Glucose variability6 and hypoglycemia duration derived from the CGMS

• Quality of life (QOL) measures

If a third transplant occurs less than 75 days after the second transplant, the 75 day endpoint data for the second transplant will not be collected.

At  $365 \pm 14$  days following the first transplant

- The proportion of subjects with an HbA1c <7.0% at Day 365 AND free of severe hypoglycemic events from Day 28 to Day 365 inclusive
- The proportion of subjects receiving a second islet transplant
- The proportion of subjects receiving a third islet transplant

A severe hypoglycemic event is defined as an event with one of the following symptoms: memory loss; confusion; uncontrollable behavior; irrational behavior; unusual difficulty in awakening; suspected seizure; seizure; loss of consciousness; or visual symptoms, in which the subject was unable to treat him/herself and which was associated with either a blood glucose level <54 mg/dL [3.0 mmol/L] or prompt recovery after oral carbohydrate, IV glucose, or glucagon administration.

At  $365 \pm 14$  days following the first and final islet transplant:

- The proportion of insulin-independent subjects
- The percent reduction in insulin requirements
- HbA1c
- MAGE
- LI
- Clarke score
- HYPO score
- Basal (fasting) and 90-min glucose and c-peptide (MMTT)
- β-score
- C-peptide: (glucose X creatinine) ratio
- AIRglu insulin sensitivity, and disposition index derived from the FSIGT test
- CGMS
- OOL
- The proportion of subjects receiving a second islet transplant
- The proportion of subjects receiving a third islet transplant
- The rate of subjects with an HbA1c  $\leq$ 7.0% and free of severe hypoglycemic events)

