## 3.1.2 Additional Hypothesis Generating Endpoints:

At  $75\pm 5$  days following the second and third transplants, the following will be reported for the subset who receive a second transplant who also have data collected and also for the subset who receive a third transplant.

- the proportion of insulin-independent subjects
- the percent reduction in insulin requirements
- HbA1c
- MAGE
- LI
- HYPO score
- Basal (fasting) and 90-min glucose and c-peptide (MMTT)
- β-score
- C-peptide: (glucose X creatinine) ratio
- Acute insulin response to glucose (AIRglu), insulin sensitivity, and disposition index derived from the insulin-modified frequently-sampled intravenous glucose tolerance (FSIGT) test
- Glucose variability and hypoglycemia duration derived from the continuous glucose monitoring system® (CGMS)
- QOL

At  $365 \pm 14$  days following the last islet transplant will include the change in the following measures from the results obtained at  $75 \pm 5$  days following the last islet infusion:

- the proportion of insulin-independent subjects
- the percent reduction in insulin requirements
- HbA1c
- MAGE
- LI
- Clarke score
- HYPO score
- Basal (fasting) and 90-min glucose and c-peptide (MMTT)
- β-score
- C-peptide: (glucose X creatinine) ratio
- Glucose variability and hypoglycemia duration derived from the continuous glucose monitoring system® (CGMS)
- QOL

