# 7.5.1 Criteria and Timing for Subsequent Islet Transplants

Islet transplant recipients who do not meet criteria for insulin independence (see section 3.1), but have either a basal or stimulated c-peptide level  $\geq 0.3$  ng/mL (0.1 nmol/L), will be considered **insulin-dependent with partial islet graft function**, and will be considered for a **second islet islet transplant**. Their insulin requirements will be determined by the total daily dose necessary to maintain the HbA1c  $\leq 7.0\%$ , the fasting capillary glucose level  $\leq 140$  mg/dL (7.8 mmol/L), and the 2-hour post-prandial capillary glucose levels  $\leq 180$  mg/dL (10.0 mmol/L), based on measuring capillary glucose levels a minimum of 21 times in a seven day period, and having at least one MAGE in that week.

In order to be eligible for a second islet transplant the following requirements must be met:

- 1. Subject received ≥5,000 IE/kg with the first transplant, but failed to achieve or maintain insulin independence
- 2. Subject has been compliant with study monitoring and prescribed immunosuppressive therapy
- 3. Subject has no unresolved SAEs
- 4. No evidence of progressive renal dysfunction, with blood creatinine rising above 2.0 mg/dL (177  $\mu$ mol/L)
- 5. No evidence of hypersensitization, allergic responses, or other potentially serious drug reactions to medications required by the protocol
- 6. PRA ≤50% by flow cytometry (assessment performed locally) and the alloantibody specificity not cross-reactive with antigen(s) present in the subsequent islet preparation in order to avoid unacceptable antigen(s).

A second islet transplant will be considered after the  $75 \pm 5$  days visit and metabolic assessment is completed, but before 8 months from the first transplant.

Islet transplant recipients who do not meet the criteria for insulin independence after the first infusion, and have both basal and stimulated c-peptide levels <0.3 ng/mL (0.1 nmol/L), will be considered for a second islet transplant only after review of the potency testing from the first transplant product and post-transplant clinical data by the Steering Committee that will have to give the final approval for the additional islet transplant.

If after the second islet transplant both basal and stimulated c-peptide levels remain <0.3 ng/mL (0.1 nmol/L), these recipients will be considered **failures** with no islet graft function, and immunosuppression will be withdrawn.

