## 7.6 Follow-up Visits

At  $75 \pm 5$  days following each islet transplant, insulin-independence will be assessed as the primary endpoint as defined above (please see Section 3.1.1) based on one week of frequent capillary blood glucose monitoring ending with a fasting clinic visit for determination of HbA1c, fasting serum glucose and c-peptide, and serum glucose and c-peptide 90-minutes after ingestion of Boost®. This information also allows for the calculation of the  $\beta$ -score, a composite index of

islet graft function. Other self-glucose monitoring information captured at this visit will enable calculation of the Clarke and HYPO scores of hypoglycemia awareness and severity, respectively, the hypoglycemia fear survey, and the MAGE and LI scores of glycemic lability. This assessment will be repeated at 6, 9, 12, 15, 18, 21, and 24 months post-transplant.

The acute c-peptide and insulin responses to IV glucose and arginine will be performed during a two night admission to the GCRC scheduled at 3 months following each transplant, and at 12 and 24 months after the last transplant. The IV glucose test will be administered as a frequently-sampled intravenous glucose tolerance test in order to calculate insulin sensitivity ( $S_I$ ) and the disposition index (DI). The IV arginine test will be performed with glucose-potentiation in insulin-independent recipients and those taking  $\leq 0.1$  U/kg of daily insulin to optimize glycemic control in order to determine the  $\beta$ -cell secretory capacity at day 75 and at 12 months. Also at 3, 12, and 24 months, 72-hours of continuous glucose monitoring will be performed.

At 6 and 14 months post-transplant, paired hypoglycemic and euglycemic clamps will be performed one week apart, in randomized order, each after a one night admission to the GCRC.

At 12 months following the first transplant retinal photography will be performed.

Clinic visits for immunosuppression drug monitoring will occur monthly for the first two years and quarterly thereafter. Additional tests will be repeated as indicated in the timeline provided in the appendix.

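### The 12-month recall part of the HYPO score is about 79% pre-transplant time at day 75, so this component can fall by day 365 without any true change

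*Protocol*

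**What the plan says.** Section 9.1.2.4 describes two parts of the HYPO score. The first is a 4-week record: "The HYPO score involves subject recording of BG readings and hypoglycemic events". The second is "recall of all severe hypoglycemic episodes in the previous 12 months".

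The Synopsis and section 3.1.1 list the "Ryan hypoglycemia severity (HYPO) score" among the secondary efficacy endpoints at 75 ± 5 days after the first and final transplants. Section 7.6 says that information "captured at this visit will enable calculation of the Clarke and HYPO scores of hypoglycemia awareness and severity", and Appendix 1 marks HYPO after transplant at days 75, 180, 270, 365 and the one-year visit after the initial transplant (Y1). Section 3.1.2 adds a hypothesis-generating set at day 365 after the last transplant, which "will include the change in the following measures from the results obtained at" day 75. HYPO and Clarke are both on that list.

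Nothing in the protocol shortens the recall after transplant or limits it to post-transplant time. By contrast, the composite of HbA1c and freedom from severe hypoglycemia counts events only from day 28 to day 365.

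**The concern.** A 12-month look-back taken 75 days after an intervention mostly covers time before it. Subjects are selected for severe hypoglycemia (inclusion criterion 7), so that earlier time will often contain episodes. Two results could then mislead. The day-75 value would partly describe history rather than graft function. The change from day 75 to day 365 would partly record old episodes leaving the window, and could be read as continuing improvement when the post-transplant course is flat, or as stability when it is worsening. Section 1.1 describes loss of graft function over time, which is what a change measured from day 75 should be able to show.

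The Clarke score has a separate problem: its change from day 75 is requested, but the schedule has no day-75 Clarke assessment.

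**Working it through.** The protocol gives no figure for the pre-transplant share, so there is none to reproduce.

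**Inputs.** Recall of 12 months, taken as 365 days, and a 28-day record (9.1.2.4). Visits at 75 ± 5 and 365 ± 14 days (3.1.1). A second transplant is considered after the 75 ± 5 day visit "but before 8 months from the first transplant" (7.5.1), and no additional transplant is allowed once 8 months of follow-up are complete. The last of several transplants therefore falls between about day 70 and day 243 after the first.

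**Share of the recall window before the index transplant**, at day d: (365 − d)/365.

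- Day 75: 290/365 = 79.5% (day 70: 295/365 = 80.8%; day 80: 285/365 = 78.1%)
- Day 180: 185/365 = 50.7%
- Day 270: 95/365 = 26.0%
- Day 365: 0% (day 351: 14/365 = 3.8%)

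**Repeat recipients.** At day 75 after a last transplant done g days after the first, the share before the first transplant is (365 − 75 − g)/365. For g = 70 this is 220/365 = 60.3%; for g = 243 it is 47/365 = 12.9%.

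**The 4-week record** at day 75 covers days 47 to 75, all after transplant.

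**Roll-off with no true change after transplant.** Let r be the ratio of the post- to the pre-transplant episode rate, constant after a single transplant. In units of the annual pre-transplant rate, the expected recalled count is (290 + 75r)/365 at day 75 and r at day 365.

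| r | Day 75 | Day 365 | Change |
|---|---|---|---|
| 0 | 0.795 | 0 | −100% |
| 0.1 | 0.815 | 0.10 | −88% |
| 0.25 | 0.846 | 0.25 | −70% |
| 0.5 | 0.897 | 0.50 | −44% |
| 1 | 1.000 | 1.00 | 0% |

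**Masking.** Take a single-transplant subject with no severe episodes up to day 75 who then returns fully to the pre-transplant rate. The expected recalled count is 290/365 at day 75 (all before transplant) and 290/365 at day 365 (all from days 75 to 365). A complete relapse shows as no change.

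**Total score.** Let w be the fraction of the day-75 score that comes from recalled episodes. With r = 0, a 4-week part that stays constant and a recall part proportional to the count, the spurious fall in the total is w: 10% at w = 0.10, 50% at 0.50, 100% at 1.0. The documents do not give w.

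**Clarke.** Section 3.1.2 asks for its change from day 75, and section 7.6 says the day-75 information "will enable calculation of the Clarke and HYPO scores". The Clarke row of Appendix 1 is marked after transplant only at days 180, 365 and Y1. The HYPO row does have a day-75 mark.

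**The case against.** The strongest reply is that 79% is a share of calendar time in one component, not of episodes and not of the score. That stands. The 4-week part is wholly post-transplant, and without weights the spurious share of the total could lie anywhere from 0 to 100%. A reader might infer that the day-75 score mainly measures pre-transplant history, or that its change to day 365 is largely artefact. The documents do not establish either.

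Other limits also stand:

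- Criterion 7 requires an episode in the 12 months before enrollment, not before transplant. Subjects then wait for an islet preparation (7.3), so the qualifying episode may already be outside the window. The effect arises only in subjects with an episode in the pre-transplant part of the recall.
- The change endpoint is labelled hypothesis-generating and is anchored on the last transplant, so the share before any transplant is smaller in repeat recipients.
- A reader might infer bias against or in favor of CIT-05 relative to CIT-07. Subjects are randomized between the studies, so with the same window in both the expected effect is dilution. Compared with baseline, carried-over history makes the day-75 HYPO result conservative.
- Section 10.2.2 already urges extreme caution with nominally significant secondary findings.

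These points limit the size and reach of the problem but do not remove it. The protocol itself fixes the window, the visits and the change measure, and caution about multiplicity does not address a shift built into the measurement.

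**Conclusion.** The point holds for the recall component. At day 75 after a first transplant, about 79% (78-81%) of its window is pre-transplant, against about 0% at day 365. When the last transplant is a repeat, about 13-60% of the day-75 window lies before the first transplant. Where that period contains episodes and the rate falls after transplant, the component drops by day 365 with no true change (44% at r = 0.5, 100% at r = 0), and it can conceal a relapse. These percentages assume a single transplant and a constant rate after it.

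The effect on the total HYPO score cannot be quantified from the protocol. One secondary endpoint and one hypothesis-generating change are affected; the primary endpoint and the day-28-to-365 severe-event endpoint are not. This should be corrected, but it does not threaten the trial's main conclusion.

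The Clarke mismatch is a separate and plain inconsistency: as scheduled, the requested change from day 75 cannot be computed.

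**What to change.** Keep the published HYPO score as defined. In sections 9.1.2.4 and 3.1.2, add that post-transplant visits will also report (a) the 4-week component alone and (b) severe episodes since the first transplant as events per person-time. State that the day-75-to-365 change will be based on (a) and (b), not on the total score. For that change, show the time up to the day-75 visit and the time from then to day 365 as separate intervals, so that they do not overlap.

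No new data are needed for HYPO: hypoglycemic events are collected from enrollment consent (8.2.1) and assessed at the scheduled visits (Appendix 1). There are two costs. These measures cannot be set against the published percentiles, which rest on the 12-month form. The 75-day rate is also imprecise with 12 subjects, since one episode in 75 days is 365/75 = 4.9 per year. Eligibility is untouched because the addition applies only after transplant.

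For Clarke, choose one of two reconciliations. Either add the eight-question survey to Visit 10 (day 75) in Appendix 1, or remove Clarke from the change list in 3.1.2 and correct 7.6. The second would match the day-75 endpoint lists in the Synopsis and 3.1.1, which omit Clarke. The first costs one short questionnaire at an existing visit; the second costs only wording.
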